### 8.1.8 Pregnancy Reporting

Participants who self-report pregnancy will be excluded from the study at screening. If the participant reports being pregnant after enrollment, they will be withdrawn from the study and a pregnancy form within the study application portal will be filled out by the PI or designee and the Sponsor will be alerted of the pregnancy.

## 9. Participant Completion and Withdrawal

### 9.1 Participant Completion and Withdrawal

Participants will have completed the study once the device is used, all post-treatment procedures are completed at stipulated timepoints, and the study device is returned.

The participant may withdraw from the study at any time by notifying the Study Team. Participants may be withdrawn from the study by the investigator if study procedures have not been followed or if the investigator determines the participant is not able to safely continue with the study due to an AE or other health-related issue.

Participants will have up to 35 days to complete the treatment session after receiving the device, after which they will have to return the device and will be withdrawn from the study.

## 10. Data Management

### 10.1 Data Collection

Study data will be collected in the ObvioHealth app. ObvioHealth will maintain accurate documentation (source data) that supports the information entered in the eCRF.

Management of clinical data will be performed in accordance with ObvioHealth's applicable standards and data cleaning procedures with oversight by the Sponsor to ensure integrity of the data, for example, to remove errors and inconsistencies in the data.

Clinical data (including AEs, concomitant medications, and expected adverse reactions data) and clinical laboratory data will be entered into ClinicalOne, a 21 CFR Part 11-compliant data capture system provided by the study Sponsor. The data system includes password protection and internal quality checks, such as automatic range checks, to identify data that appear inconsistent, incomplete, or inaccurate. Clinical data will be automatically transferred from the ObvioGo Platform into ClinicalOne via a continuous API integration.

In addition to clinical data, device performance data is extracted and reviewed once the Mi-Helper device body is returned post treatment. These logs include treatment start and stop time, confirmation of the flow rate, back pressure, humidity, and any voluntary or involuntary treatment interruptions. This data will be accessible by the unblinded sponsor team

representative. All data points except flow rate will be entered into the ClinicalOne EDC by an unblinded study team member.

To protect the privacy of participants, no personal information (including the participant's name or initials) is to be recorded in the eCRF or as part of the query text. Identifiable data are isolated to a special team at ObvioHealth and these data will not be transferred/available to the Sponsor.

The Sponsor will obtain and retain all eCRFs and associated study data as applicable at the completion of the study.

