## 5. Study Design

### Overview

This is a prospective, double-blind, sham-controlled, randomized clinical trial. This study aims to assess the efficacy and safety of the Mi-Helper transnasal neuromodulation device for acute treatment of migraine in an at home setting.

Treatment Assignment Blinding for this study will be applied to the PI and the study team. The team members who are directly involved in the analysis of the study results, including the biostatistician, will also be blinded. Only the designated group of team members directly involved in overseeing the logistical and distribution aspects of the study products will be unblinded. As needed, the PI may be unblinded in case of an AE/SAE that may impact participant safety. If the unblinding occurs inadvertently or through PI's need due to an AE/SAE impacting participant safety, that event will be noted as a protocol deviation.

Adults aged 18 years to 70 years old ,inclusive, with a diagnosis of migraine (with or without aura) for at least one year will be recruited for this study.

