## 7. Study Intervention

### 7.1 Study Product Description

#### 7.1.1 Test and Sham Device Description

##### **Test Device Description**

Mi-Helper has been designed for use in an at-home setting, whenever patients feel the onset of a migraine attack. The device delivers a controlled stream of dry air into the nose. The air is mixed with a fine saline mist for added comfort and efficiency. It is a lightweight, low-cost device with an integrated nebulizer, disposable tube set and desiccant cartridge. It is software controlled.

The Mi-Helper neuromodulation device is intended for acute treatment of migraine, with or without aura, in adult patients.

The Mi-Helper device is small and lightweight, weighing 7 lbs. It is designed to sit on a tabletop next to an afflicted individual. This device produces a low flow of dry, filtered air to induce neuromodulation via local evaporative cooling in the nasal turbinates. This air flow is delivered through a handheld nebulizer and air hose connected to the device. The nebulizer delivers ultrasonic misting to keep the turbinates moist and facilitate continued evaporative cooling. The nebulizer sits at the entrance of the nose and does not cannulate into the nostrils. The handpiece can be connected to the side of the device via a magnet when not in use.

The primary functional component inside the device is a blower which generates the flow of air. Inlet air is pulled into the device from the local ambient room air; the internal blower is then used to pump the air across a desiccant material to extract any moisture from the incoming air stream. The desiccant material is in a disposable cartridge that is placed into the Mi-Helper at the time of treatment.

Once treatment is initiated, the flow of air enters the individual's nostril and exits the other nostril, inducing an evaporative cooling energy exchange in the turbinates and upper airway. The blower inside the device provides the motive force to move the air supply over the desiccant material and across the individual's turbinates. The Mi-Helper will deliver treatment for 15 minutes and will turn off once the treatment is complete.

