### **Sham Device Description**

The sham treatment will be administered through the Mi-Helper device using cartridges that contain inactive material of comparable size and weight as the active desiccant material, which will not dehumidify air entering the blower. Additionally, participants will receive less than 2 LPM of air flow, with the device blower cycling on and off periodically (approximate period of active flow will be 70% of the time) during the 15-minute treatment session.

[figure not shown]

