## **10.3 Computerized Edit Checks**

The database will incorporate the needed programmed edit checks to ensure consistent and complete data entry. The data management team will perform edit checks as the data are being entered into the system, and queries will be entered on a Data Issues Log for the decentralized site staff to address. The data manager will raise queries as needed on safety data to code the terms (AEs and Drugs or concomitant medication) appropriately.

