## 12. Quality Control and Assurance

## 12.1 Acceptability of Case Report Forms (Source Documents)

A case report form is a printed, optical, or electronic document designed to record the protocol required information to be reported to the sponsor on each trial participant. This study will utilize electronic Case Report Forms (eCRFs) within the ClinicalOne Electronic Data Capture (EDC) platform.

All study data, including electronic patient reported outcomes, will be collected in the ObvioHealth Study App, ObvioGo. Such data will be transferred from the ObvioHealth study platform to the oracle ClinicalOne EDC to be stored in eCRFs. ObvioHealth will provide data management services for this protocol, with SPRIM PRO providing site-based services.

The study team will maintain accurate documentation (source data) that supports the information entered in eCRF. To protect the privacy of participants, no personal information (including the participant's name or initials) is to be recorded in the eCRF or as part of the query text. Personally Identifiable data will not be transferred/available to the Sponsor.

The study monitor will perform ongoing review of the eCRFs in accordance with the monitoring plan, to confirm that data entered into the eCRF by authorized site personnel are accurate, complete, and verifiable from source documents; that the safety and rights of participants are being protected; and that the study is being conducted in accordance with the currently approved protocol and any other study agreements, ICH GCP, and all applicable regulatory requirements.

All source data should be reviewed by the study staff and the study monitor to ensure accurate transcription of data and that any potential AEs or concomitant medications reported on these documents are discussed with the participant and transcribed accurately to the eCRF and/or DMS. ePROs that are classed as source data will be retained by the investigator and true/certified copies may be sent to the Sponsor or a designated vendor as required. Any AEs or concomitant medications collected as ePRO will be reviewed and transcribed to the eCRF by a member of the study team.

The Sponsor will obtain and retain all eCRFs and associated study data at the completion of the study.

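### Only flow rate is kept out of the EDC; back pressure and humidity from the same device log may also reveal the arm, and no viewing limit is stated

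*Protocol*

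**What the plan says.** Protocol 10.1 describes a performance log extracted after the device body comes back. Besides treatment start and stop time, it holds "confirmation of the flow rate, back pressure, humidity, and any voluntary or involuntary treatment interruptions". The extracted log is open to an unblinded sponsor representative. The rule for the database follows: "All data points except flow rate will be entered into the ClinicalOne EDC by an unblinded study team member".

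The arms differ in what the log measures. The active device uses its blower to "pump the air across a desiccant material to extract any moisture from the incoming air stream" and delivers 10 LPM (Protocol 7.1.1 and 11.2). The sham cartridge holds inactive material "which will not dehumidify air entering the blower". Sham flow is under 2 LPM, "with the device blower cycling on and off periodically", with flow on for about 70% of the 15 minutes (Sham Device Description).

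On blinding, Protocol 5 (Overview) states: "Treatment Assignment Blinding for this study will be applied to the PI and the study team". It extends the blind to those analysing the results, including the biostatistician. SAP 4.1 repeats this and adds the sub-investigator.

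The PI assesses each AE individually (Protocol 8.1.3). Relatedness categories are to be assigned before database lock (Protocol 11.7, SAP 9), and the primary safety outcome is the incidence of device-related AEs to 48 hours.

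**The concern.** Withholding flow rate is sensible, and it has a purpose only if people under the blind can read the EDC. Other sections suggest that they can. On data checks, Protocol 10.3 says "queries will be entered on a Data Issues Log for the decentralized site staff to address". On safety data, Protocol 12.1 says "Any AEs or concomitant medications collected as ePRO will be reviewed and transcribed to the eCRF by a member of the study team". Corrections are endorsed by the Investigator (10.2), and the monitor reviews eCRFs throughout (12.1). If back pressure or humidity can stand in for flow rate, the safeguard removes one indicator of the arm and leaves others in the same database.

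The judgement at stake is device-relatedness. A rating made or revised with arm-revealing data at hand could move in either direction, so any bias need not be towards no difference. Per-protocol membership turns partly on whether a deviation counts as major (Protocol 11.3, SAP 6.1.3), and neither document says when that call is made or under what blind. Per-protocol is only a sensitivity set, so less depends on it.

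**Working it through.** The point rests on how sections read together; the plan gives no figure for it. The sample size (58 evaluable per group, 156 randomised) is not affected.

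**1. Log items against the arms**

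| Log item | Active | Sham | Entered in EDC? |
|---|---|---|---|
| Flow rate | 10 LPM | under 2 LPM, on about 70% of the time | No |
| Back pressure | not given; plausibly follows flow | not given; plausibly follows flow | Yes |
| Humidity | dried air | undried air | Yes |
| Start and stop time | 15 min session | 15 min session | Yes |
| Interruptions | not given | not given; blower cycles by design | Yes |

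**2. How far apart the arms are in flow** (Protocol 11.2 and Sham Device Description)

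- While the blower runs: 10 / 2 = 5, so at least 5-fold.
- Averaged over the session, taking 2 LPM as the ceiling during the on-phase: 2 × 0.70 = 1.4 LPM, and 10 / 1.4 = 7.1, so at least 7.1-fold.
- Time without flow on sham: 15 × 0.30 = 4.5 minutes.

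These ratios concern flow. How much of the separation reaches the recorded back pressure depends on the sensor and the airway, which the documents do not describe. Humidity differs by arm only if it is measured downstream of the cartridge; measured at the room-air inlet, it would not.

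**3. Who may see the entered fields**

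Protocol 10.1 names unblinded roles for reading the extracted log and for entering it. Neither the protocol nor the SAP says who may view the fields once they are in ClinicalOne.

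**4. Timing**

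- The primary efficacy endpoint is self-reported 2 hours after treatment. Device return is prompted only after the 24-hour assessment (Protocol 5, End of Study Procedures), so the log cannot influence it.
- The PI or a designee contacts the participant within 1 business day of a reported health change (8.1.3). Many first AE assessments will therefore precede the log.
- AE observation runs to study completion (8.1.3), and completion includes device return (9.1). Late reports and later revisions can therefore coincide with the log being available.

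**5. What one call is worth**

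These are effects of a single hypothetical decision, not estimates of bias.

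- Related-AE incidence, if the changed rating concerns that participant's only related AE: 1/78 = 1.3 points on all randomised in an arm, or 1/58 = 1.7 points if only the planned evaluable number is treated.
- Per-protocol difference at the planned rates, taking 58 per arm: 0.41 × 58 = 23.8, about 24 responders on active; 0.16 × 58 = 9.3, about 9 on sham.
  - Excluding one active non-responder: 24/57 − 24/58 = 0.4211 − 0.4138 = 0.0073, adding 0.7 points to the difference.
  - Excluding one sham responder: 9/58 − 8/57 = 0.1552 − 0.1404 = 0.0148, adding 1.5 points.

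**The case against.** The sponsor could fairly say that the important steps are already protected. The raw log goes to an unblinded representative, entry is by an unblinded person, the PI is blinded, and AE categories are set before lock. Changes need a rationale and leave an audit trail (Protocol 10.2 and 10.4). The study team includes some unblinded members (8.1.3, 12.4), so a reference to the study team does not show that a blinded person opens the device form. Queries on device fields could go back to whoever entered them. Viewing rights are often set in operational plans, and the protocol refers to a monitoring plan and a product management plan that are not available here. The log items could also be confirmation checks rather than raw readings.

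Most of this stands, and it limits the claim. A reader might infer that the PI will see arm-revealing data, or that the blind has failed. The documents do not support that: none of the text shows a blinded person viewing these fields, and none gives readings by arm. A reader might also infer that the efficacy result is at risk; the timing above rules that out for the primary endpoint.

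Two things remain. Limits on who extracts and enters the data do not limit who reads them afterwards. An audit trail records a change of rating but does not keep the rater blind. If a role restriction exists elsewhere, stating it in 10.1 takes one sentence.

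**Conclusion.** The point holds as a gap in a safeguard that the sponsor evidently intended. The protocol withholds flow rate but enters two fields that may carry the same information, and it states no viewing limit while relatedness ratings and per-protocol calls can still be open. It is a plausible exposure, confined to late or revised relatedness ratings and deviation calls.

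How often it would occur, and its net effect, cannot be estimated from the documents. No success threshold is stated for safety, so no formal decision changes. The conclusion rests on two assumptions: that recorded back pressure follows flow, or humidity is sensed after the cartridge; and that no role restriction is set in a plan not seen here. If either fails, the point reduces to a wording clarification. Importance is low: an optional, cheap improvement.

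**What to change.** Replace the sentence in Protocol 10.1 with:

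> Until database lock and unblinding, flow rate, back pressure and humidity are held in a restricted file, or in EDC fields visible only to unblinded roles. Treatment start and stop time, session completion, and voluntary and involuntary interruptions (excluding programmed blower cycling) are entered in the EDC by an unblinded study team member.

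The exclusion of programmed cycling matters because the sham blower stops by design; logged as interruptions, those stops could themselves identify the arm. If back pressure or humidity values are already in the EDC, restrict both the fields and their audit history to unblinded roles, since the audit trail keeps original entries.

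Add to Protocol 11.3 and 11.7, and to SAP 6.1.3 and 9, that AE relatedness and per-protocol membership are finalised before lock by people without access to the restricted fields.

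The cost is one rewritten sentence and short additions in four places. Unblinded staff already extract and enter the log. Endpoints, tests, sample size and analysis-set definitions do not change. The one drawback is that queries on the restricted device data must go through the unblinded representative.

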## **10.2 Data Handling**

Documentation of all data management activities should allow step-by-step retrospective assessment of data quality and study performance.

Any changes or corrections to data will be performed in the Oracle Clinical One Electronic Data Capture Platform and will include rationale for changes. The EDC system has an audit trail, which will provide a complete record of the changes and corrections endorsed by the Investigator.

AEs will be coded using Medical Dictionary for Regulatory Activities (MedDRA).

## **10.3 Computerized Edit Checks**

The database will incorporate the needed programmed edit checks to ensure consistent and complete data entry. The data management team will perform edit checks as the data are being entered into the system, and queries will be entered on a Data Issues Log for the decentralized site staff to address. The data manager will raise queries as needed on safety data to code the terms (AEs and Drugs or concomitant medication) appropriately.

## **10.4 Audit Trail**

The clinical Data Management System (DMS) complies with Good Clinical Practice (GCP) predicated rule requirements, laws and regulations (Personal data protection) for clinical trials and allows an audit of actions performed by users.

All original entries and changes made in the database will be captured by an audit trail which will include the date and time of the entry or change, and the individual making the entry or change who will be identified via their unique user ID.

# **11. Statistical Analysis**

## **11.1 Determination of Sample Size**

The sample size for this study was calculated to test the null hypothesis with Fisher's exact test.

The sample size is calculated to test the null hypothesis with 80% power at a 5% level of significance using PASS 2024 software, version 24.0.2.

If we assume that 41% of the subjects in the active treatment arm will have pain freedom at 2 hours post treatment versus 16% in the sham arm, then 116 evaluable subjects are required (58 per group). Allowing for a 25% dropout rate, a total of 156 (78 active versus 78 sham) subjects should be enrolled in the study.

## 11.2 Randomization

For this study, a total of 156 participants will be randomized equally into two groups:

- Group I (active treatment): 10 LPM, dehumidified air, 15 minutes
- Group II (sham [control] treatment): 2 LPM, ambient air administered intermittently via Mi-Helper, 15 minutes total

Following randomization, balance between the two arms will be evaluated and confirmed using standardized mean differences (SMD), where absolute SMD values less than 0.2 will be considered as indicating good balance on a given variable or confounder. Subjects will be randomized in a 1:1 fashion, with stratification for gender.

## 11.3 Populations for Analyses

- **Intent-to-Treat (ITT) Population** – all participants who were randomly assigned to a treatment.
- **Modified Intention to Treat (mITT) Population** – all participants who used the study intervention and completed a baseline and 2-hour post-dose pain assessment.
- **Per Protocol (PP) Population** – all participants in the mITT population who do not have a major protocol deviation related to primary endpoint and complete the treatment in compliance with the protocol, with group assignment as treated, and have no use of rescue medication within 2 hours post treatment.

The ITT analysis set will serve as the main analysis set for all safety evaluations.

The mITT analysis set will be the primary population used for efficacy analyses in this study.

The primary and secondary efficacy assessments will also be performed on the PP and the ITT analysis sets as a sensitivity analysis.

## 11.4 General Considerations

All statistical analyses will be performed using Stata software (version 19, StataCorp LLC, College Station, Texas).

The Pearson chi-squared test will be used to compare randomized arms with regards to primary and secondary endpoints. Logistic regression modeling will estimate odds ratios and

95% confidence intervals for pain relief/ freedom endpoints to compare the two groups. The absolute difference in rates of freedom from pain will be estimated with 95% confidence intervals. Binomial exact 95% confidence intervals will be constructed for the incidence of primary and secondary endpoints within each group.

Deviations from the planned analysis will be described, with proper justification, in the clinical study report.

## 11.5 Significance Level and Handling of Type I Error

Type I Error: The overall significance level for this study is 5% using two-tailed tests

Hierarchy Approach for Secondary Endpoint Analysis: A hierarchical testing approach will be employed using a fixed-sequence procedure to control type I error due to multiple endpoint testing. The primary endpoint will first be tested and only if  $p < 0.05$ , will the secondary endpoints be tested. Testing will proceed sequentially, and each endpoint must achieve statistical significance at the 0.05 level to proceed to the next endpoint. If any endpoint in the sequence fails to achieve significance, all subsequent endpoints will not be formally tested and will be considered exploratory.

## 11.6 Efficacy Analysis

The Chi-square test will be used to compare randomized arms with regards to primary and secondary endpoints. Logistic regression modeling will estimate odds ratios and 95% confidence intervals for pain relief/ freedom endpoints to compare the two groups. The absolute difference in rates of freedom from pain will be estimated with 95% confidence interval. Binomial exact 95% confidence intervals will be constructed for the incidence of primary and secondary endpoints within each group

